PATCH 3 Inclusion (Sub-Study 2): Currently employed as a health care worker ([name]; Doctor of Osteopathic Medicine, DO; Nurse Practitioner, NP; Physician's Assistant, PA; and [name] or other members of the medical care team with significant COVID-19 exposure); asymptomatic and presumed negative for COVID-19 (no confirmatory testing conducted); scheduled for an average of ≥ 20 hours per week of clinical care over the next two months (or equivalent indicating at least part-time employment). Participant will be asked to comply with their employer's potential or confirmed COVID-19 incident protocol and must agree to undergo COVID-19 testing per standard of care using an FDA approved method upon the presentation of symptoms indicative of an influenza like illness; if a confirmatory COVID-19 diagnosis is given, participant will be offered to cross-over to HCQ 600 mg qd for 14 days. At the end of the 60-day medication period, participants remaining undiagnosed for COVID-19 will undergo virus and serology testing. (See Appendix- PATCH3 process flows)

PATCH 2 & PATCH 3 Combined Exclusion Criteria

(See Study Exclusions and Content Job Aid)

- Allergy to hydroxychloroquine, 4 aminoquinolines, or quinine
- Known G6PD deficiency
- Pregnant or lactating or intention of becoming pregnant during the study as self-reported during enrollment screening
- Receiving any trial treatment drug for 2019-nCoV within 14 days prior to screening evaluation (off label, compassionate use or trial related)
- Known retinal disease including but not limited to macular degeneration, retinal vein occlusion, visual field defect, diabetic retinopathy
- History of interstitial lung disease severe emphysema or asthma, or chronic pneumonitis Current diagnosis of porphyria or psoriasis
- Serious intercurrent illness that requires active intravenous therapy, intense monitoring, or frequent dose adjustments for medication including but not limited to infectious disease, cancer, autoimmune disease, cardiovascular disease

PATCH 2 & 3 TRIAL

- Have undergone major abdominal, thoracic, spine or CNS surgery in the last two months, or plan to undergo surgery during study participation
- Is receiving cytochrome P450 enzyme-inducing anticonvulsant drugs (i.e. phenytoin, carbamazepine, Phenobarbital, primidone or oxcarbazepine) within four weeks of the start of the study treatment
- Currently taking digoxin
- History or evidence of increased cardiovascular risk including any of the following:

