10.2 Hospitalization, Prolonged Hospitalization or Surgery

Any adverse event that results in hospitalization or prolonged hospitalization should be documented and reported as a serious adverse event unless specifically instructed otherwise in this protocol. Any condition responsible for surgery should be documented as an adverse event if the condition meets the criteria for an adverse event.

Neither the condition, hospitalization, prolonged hospitalization, nor surgery are reported as an adverse event in the following circumstances:

- Hospitalization or prolonged hospitalization for diagnostic or elective surgical procedures for a preexisting condition. Surgery should not be reported as an outcome of an adverse event if the purpose of the surgery was elective or diagnostic and the outcome was uneventful.
- Hospitalization or prolonged hospitalization required to allow efficacy measurement for the study.
- Hospitalization or prolonged hospitalization for therapy of the target disease of the study, unless it is a worsening or increase in frequency of hospital admissions as judged by the clinical investigator.

Expected adverse events are those adverse events that are listed or characterized in the Package Insert or current Investigator Brochure.

Unexpected adverse events are those not listed in the Package Insert (P.I.) or current Investigator Brochure (I.B.) or not identified. This includes adverse events for which the specificity or severity is not consistent with the description in the P.I. or I.B. For example, under this definition, hepatic necrosis would be unexpected if the P.I. or I.B. only referred to elevated hepatic enzymes or hepatitis.

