15.2 Response Criteria

PATCH 2 (Sub-Study 1): Measurement of SARS-CoV-2 positivity confirmed by an accepted testing method. Rate of hospitalization will be defined by a hospitalization occurring within 30 days of the date of participant enrollment.

PATCH 3 (Sub-Study 2): Rate of COVID-19 infection will be defined by measurement of SARS-CoV-2 identified by accepted testing methods.

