Appendix 3: PATCH 2 Job Aid

PATCH2 STUDY LEAD JOB AID

A PATCH2 AUTOMATIC STUDY EXCLUSIONS	
Consumer Language for Enrollment Exclusions 
 These exclusions are automatic during the online enrollment experience in the enrollment portal If indicated exclusion response is selected, it is an automatic exclusion from the study 	Automatic Portal Exclusion
Are you between the ages of 50-75? [yes/ no]	If NO
Have you had a fever within the last four days? [yes/ no]	If NO
Do you require hospitalization? [yes/ no]	If YES
Are you able to self-quarantine at home for 14 days? [yes/ no]	If NO
Have you been tested for COVID-19? [yes/ no]	If NO

B AUTOMATIC CLINICAL EXCLUSIONS		
Consumer Language for Enrollment Exclusions 
 These exclusions are automatic during the online enrollment experience in the enrollment portal If “yes” to any, it is an automatic exclusion from the study. 	Automatic Portal Exclusion	
Protocol Language: Allergy to hydroxychloroquine, 4 aminoquinolines, or quinine	Do you have an allergy to hydroxychloroquine (HCQ), aminoquinolines, or quinine? [yes/ no]	X
Protocol Language: Patients with G6PD deficiency	Do you have a G6PD deficiency? [yes/ no]	X
Protocol Language: Pregnant or lactating or positive pregnancy test during pre-medication examination	Are you pregnant? [yes/ no]	X
	Are you breast feeding? [yes/ no]	X
Protocol Language: Receiving any trial treatment drug for 2019-ncov within 14 days prior to screening evaluation (off label, compassionate use or trial related)	Have you been in any other drug trial for COVID-19? [yes/ no]	X
Protocol Language: Patients with serious intercurrent illness that requires active infusional therapy, intense monitoring, or frequent dose adjustments for medication including but not limited to infectious disease, cancer, autoimmune disease, cardiovascular disease.	Are you on any IV or other serious medications, such as chemotherapy? [yes/ no]	X
Protocol Language: Patients who have undergone major abdominal, thoracic, spine or CNS surgery in the last 2 months, or plan to undergo surgery during study participation.	Have you had any surgery in the last two months? [yes/ no]	X
Protocol Language: Patients currently taking digoxin	Do you take the medication, digoxin or lanoxin? [yes/ no]	X
(From Medication Section)	Have you ever had a seizures? [yes/ no]	X
(From Medication Section)	Have you ever had a transplant? [yes/ no]	X

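### The portal asks about past surgery but not the planned surgery that 3.1 also excludes, so an operation booked for about days 15 to 30 can be scored as a PATCH 2 primary event (minor)

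*Combined protocol and SAP*

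**What the plan says.** The combined exclusion list in section 3.1 has a two-part surgical criterion: "Have undergone major abdominal, thoracic, spine or CNS surgery in the last two months, or plan to undergo surgery during study participation". The synopsis repeats it.

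Table B of the PATCH 2 job aid (Appendix 3) prints the criterion with its second part, "or plan to undergo surgery during study participation". The question the applicant answers is "Have you had any surgery in the last two months? [yes/ no", with yes as the exclusion. Table B of the PATCH 3 job aid (Appendix 4) has the same row and the same question.

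Two other PATCH 2 portal questions bear on future admissions: "Do you require hospitalization? [yes/ no" and "Are you able to self-quarantine at home for 14 days? [yes/ no". The disease and medication questions that lead to a live conversation (part C of the job aid) do not mention surgery. Item 2 of the PATCH 2 procedure in 4.0 calls for a review of the eligibility criteria before consent and randomisation; its text names only age, fever and testing.

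On the endpoint, 15.2 says for PATCH 2: "Rate of hospitalization will be defined by a hospitalization occurring within 30 days of the date of participant enrollment". It states no cause and no exception. Section 10.2 lists, among the events not reported as adverse events, "Hospitalization or prolonged hospitalization for diagnostic or elective surgical procedures for a preexisting condition". Section 16.1 describes the outcome as recovery with no need for hospital care and tests the odds ratio for recovery among test-positive patients.

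**The concern.** The automatic screen passes people whom the protocol excludes. The question is stricter than 3.1 about the past, since it asks about any surgery where 3.1 lists major operations at named sites, and silent about the future. The same table splits another two-part criterion, pregnancy and lactation, into two questions, so the missing half looks like an oversight.

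The gap reaches the primary outcome because 15.2 makes no distinction between an admission for worsening illness and one booked beforehand. A booked operation cannot respond to study drug. Each one counted adds background events to both arms and pulls the odds ratio towards 1. The HCQ arm is most sensitive, because the plan expects only 50 × 0.05 = 2.5 events there. Section 10.2 shows that the authors separate elective admissions for safety reporting, but 15.2 does not say whether the endpoint does the same.

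**Working it through.** **Who can get through (PATCH 2)**

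- Past surgery: asked, excluded if yes.
- Present need for admission: asked, excluded if yes.
- Admission booked within about 14 days: no direct question, but a truthful answer to the quarantine question should exclude it.
- Admission booked for about days 15 to 30: no readable portal question. Only the general review in 4.0 item 2 stands in the way.

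The last group falls inside the 30-day window of 15.2.

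**Inputs (16.1)**

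Hospitalized: placebo 30%, HCQ 5%. Test-positive patients: 50 per arm. One-sided alpha 0.05. Stated power: at least 90%.

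**The plan's own figure**

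Pooled two-proportion test, with mean proportion 0.175:

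- numerator: √50 × 0.25 − 1.645 × √(2 × 0.175 × 0.825) = 1.768 − 0.884 = 0.884
- denominator: √(0.30 × 0.70 + 0.05 × 0.95) = 0.507
- power = Φ(1.742) = 0.959

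Wald test on the log odds ratio, the scale named in 16.1:

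- log OR = ln 8.14 = 2.097
- SE = √[(1/50)(1/0.21 + 1/0.0475)] = 0.719
- power = Φ(2.919 − 1.645) = 0.899

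The stated 90% is therefore reproduced, comfortably or almost exactly, depending on the test.

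**Adding planned admissions**

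The documents give no rate of planned admission. Assume a proportion e, equal in both arms and independent of illness-related admission. Then placebo = 0.30 + 0.70e and HCQ = 0.05 + 0.95e. The three-look columns are simulations at 17, 34 and 50 per arm with the printed efficacy and futility bounds.

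| e (assumed) | Placebo | HCQ | Odds ratio | Fixed-sample power, pooled | Three-look, pooled | Three-look, log OR |
|---|---|---|---|---|---|---|
| 0 | 0.3000 | 0.0500 | 8.14 | 0.9592 | 0.9678 | 0.9606 |
| 0.5% | 0.3035 | 0.0548 | 7.52 | 0.9545 | 0.9629 | 0.9552 |
| 1% | 0.3070 | 0.0595 | 7.00 | 0.9495 | 0.9575 | 0.9485 |
| 2% | 0.3140 | 0.0690 | 6.18 | 0.9388 | 0.9452 | 0.9351 |

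At e = 2% the loss is 2.0 points in the fixed-sample pooled formula and 2.3 to 2.6 points in the three-look simulations. On the fixed-sample Wald scale, z = 1.821/0.636 = 2.864, so power is Φ(1.219) = 0.889, about 1 point below 0.899.

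**Scale of the shift**

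- Extra primary events, HCQ arm: 50 × 0.95e = 0.24 to 0.95 for e = 0.5% to 2%.
- Extra primary events, placebo arm: 50 × 0.70e = 0.18 to 0.70.
- Shift in log OR: ln(8.14/7.52) = 0.08 to ln(8.14/6.18) = 0.28, or 0.11 to 0.38 of the 0.719 standard error.
- Risk difference: 0.25(1 − e), so 25.0 points becomes 24.5 at e = 2%.
- Chance of at least one planned admission among 100 analysed patients: 1 − (1 − e)^100 = 39% to 87%.

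**The case against.** The portal is not the only safeguard. Section 3.1 governs, 4.0 item 2 calls for a criteria review before randomisation, and the study lead holds a live consent call with the full criterion printed in the job aid. The enrolment flowcharts are not shown and could hold another check. This stands as a limit on how often the gap would matter. It does not close the gap, because nothing readable shows planned surgery being asked about.

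Section 16.1 points to illness-related admission, so a recovered patient who attends a booked operation does not clearly fail that outcome. This also stands: 15.2 and 16.1 can be read differently, and the plan does not say which reading applies. All-cause admission is itself a legitimate endpoint that needs no adjudication, so leaving planned admissions in is not an error if it is chosen and stated.

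Capture is uncertain too. Portal self-reporting stops after Day 14, and 10.2 exempts elective admissions from adverse event reporting. A booked admission on days 15 to 30 may never be recorded, which lowers the likely number of such events but makes the count depend on how each admission comes to light.

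Two stronger readings are tempting. A reader might infer that planned admissions bias the trial towards one arm or inflate the false-positive rate. The double-blind 1:1 randomisation does not support that; the expected effect is dilution. A reader might also infer that the same admissions contaminate the PATCH 3 hospitalization outcome. The documents do not support that either: the 30-day definition in 15.2 is given for PATCH 2 only, and PATCH 3 hospitalization is a secondary outcome that 15.2 does not define. For PATCH 3 the point is limited to the missing screening question.

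**Conclusion.** The mismatch between 3.1 and the portal question is real in both job aids. In PATCH 2 it can let a person with an operation booked for about days 15 to 30 be randomised against 3.1 and, on the wording of 15.2, counted as a primary event. The consequence is minor: at an assumed 0.5% to 2% the odds ratio falls from 8.1 to about 7.5 to 6.2, well within its sampling error, with a power loss of about 2 points or less by the fixed-sample pooled formula and up to 2.6 points by simulation.

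This rests on an assumed rate that is equal in the two arms, on truthful answers to the quarantine question, and on the readable text alone. The documents do not support higher rates in recently febrile, test-positive patients who have passed the quarantine question and a criteria review.

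**What to change.** Add to Table B of both job aids a question that applies the second half of the existing 3.1 criterion, for example *Are you planning any surgery during the study period?*, with yes as the exclusion. This enforces a rule the protocol already has.

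Secondarily, bring 15.2 into line with 16.1 by stating, before unblinding, whether an admission for a procedure scheduled before enrolment counts as a PATCH 2 primary event. Record the reason for each admission through day 30, so that the rule can be applied the same way to every patient.

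The cost is one portal question, one sentence and one data field. The only applicants turned away are those whom 3.1 already excludes.

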Side effects occurring at a frequency which cannot be estimated from available data	
 • Convulsions • Heart problems (e.g. breathlessness with exercise or even at rest, swelling of the legs, ankles and feet, irregular heartbeats that feel rapid or pounding, chest pain, sudden fainting) • Hypoglycemia (low blood sugar) (e.g. sweating, shakiness, weakness, dizziness, fast heartbeat, nausea, irritability, blurred vision, confusion, loss of consciousness) • Increased sensitivity to sunlight. Skin rash due to sunlight can be reduced by appropriate use of sunscreen creams • Liver problems with symptoms such as: unusual tiredness, nausea, vomiting, abdominal pain, or jaundice (yellow discoloration of the eyes or skin) • Long-lasting involuntary muscle contraction; impairment of voluntary movements, tremor • Lowered blood cell counts (e.g. fatigue, weakness, increase susceptibility to infections or bleeding) • Muscle weakness • Psychosis (e.g. hallucinations, loss of contact with reality) • Severe breathing problem (bronchospasm, angioedema) • Severe skin problem • Suicidal thoughts
Rare	Protocol Language
These occurring in 0.1 to 1% of participants receiving this drug	
 • Dizziness • Hair loss or bleaching of hair • Loss of skin pigment or increase in skin pigment (bluish-black color) • Nerve and muscle disorders (e.g. tingling, numbness, burning pain, weakness, cramps, and spasms) • Ringing in the ears, decreased hearing
Common	Protocol Language
These occur in 1 to 10% of participants receiving this drug	
 • Diarrhea • Vomiting • Loss or lack of appetite (anorexia) • Headache • Nervousness, emotional changes • Rash, itchy rash • Visual problem: blurred vision, difficulty focusing, seeing halos around lights, especially at night, seeing light flashes and streaks, night blindness, visual field loss, change in eye color (eye pigmentation), difficulty focusing eye, difficulty reading (skipped words). • Notes on Vision: HCQ may rarely cause problems with your vision. A review of over 1000 patients taking HCQ found that this side effect occurred in only 1 patient and only after they had taken the drug for 7 years. Vision problems include visual disturbances such as flickering or flashing lights, dimming of your vision (things appear darker) and decreased vision that could progress to blindness.
Very Common	Protocol Language
These occur in 10% or more of participants receiving this drug	
 • Nausea • Stomach pain • Stomach cramps

F. PATCH2 PATIENTS WELCOME BOX

Content	Description
	
THE MEDICATION BOTTLE
 
Blinded - 56 tabs
 
Protocol number: UHG R&D 2020-0003
 
Medication ID: [bottle serial number]
 
Contents: 56 tablets
 
Directions: Take two tablets by mouth every morning and every evening for 14 days
 
Store at [insert storage instructions from the manufacturer]
 
Caution: New Drug - Limited by Federal (or United States) law to investigational use

	
THE HYDROXYCHLOROQUINE MEDICATION GUIDE
 
 The HCQ Medication Guide opens with: “You have received your medication tablets in this box. These tablets may be a placebo or they may be the active hydroxychloroquine (HCQ) medication. Below is a list of possible side effects from taking active HCQ.” This guide will be shipped in the welcome kit that comes via courier in the overnight package from CSM.
	
THE STUDY JOURNAL
 
 15 page Study Journal Includes a variety of study information, contact information, FAQ, reminders and study tracking examples Will be shipped in the welcome kit that comes via courier in the overnight package from CSM
	
A THERMOMETER
 
 A thermometer will be sent to all patient participants. It will be all white
	
PEN
 
 This ink pen will be shipped in the welcome kit that comes via courier in the overnight package from CSM

E FREQUENTLY ASKED QUESTIONS (FAQ)

Type of Question	Question	Response
Study Info	What will be expected of me if I decide to participate in this study?	A package will be sent to you with either HCQ active or placebo pills. We ask that you take your medication according to the package direction, check your temperature twice daily, record and report any adverse events, and upload this information daily through the study portal at patchstudy.com for the full duration of this study. You'll also be asked to get your swab samples taken at the end of the study.

Appendix 4: PATCH 3 Job Aid

PATCH3 STUDY LEAD JOB AID

A PATCH3 AUTOMATIC STUDY EXCLUSIONS	
Consumer Language for Enrollment Exclusions 
 These exclusions are automatic during the online enrollment experience in the enrollment portal If indicated exclusion response is selected, it is an automatic exclusion from the study 	Automatic Portal Exclusion
Are you a health care worker scheduled to working an average of 20 hours a week for the next 2 months?	If NO
Are you currently asymptomatic and presume not to have COVID?	If NO
Have you had a fever within the last four days? [yes/ no]	If NO
Do you require hospitalization? [yes/ no]	If YES
Are you able to self-quarantine at home for 14 days? [yes/ no]	If NO
Have you been tested for COVID-19? [yes/ no]	If NO

B AUTOMATIC CLINICAL EXCLUSIONS		
Consumer Language for Enrollment Exclusions 
 These exclusions are automatic during the online enrollment experience in the enrollment portal If “yes” to any, it is an automatic exclusion from the study. 	Automatic Portal Exclusion	
Protocol Language: Allergy to hydroxychloroquine, 4 aminoquinolines, or quinine	Do you have an allergy to hydroxychloroquine (HCQ), aminoquinolines, or quinine? [yes/ no]	X
Protocol Language: Patients with G6PD deficiency	Do you have a G6PD deficiency? [yes/ no]	X
Protocol Language: Pregnant or lactating or positive pregnancy test during pre-medication examination	Are you pregnant? [yes/ no]	X
	Are you breast feeding? [yes/ no]	X
Protocol Language: Receiving any trial treatment drug for 2019-ncov within 14 days prior to screening evaluation (off label, compassionate use or trial related)	Have you been in any other drug trial for COVID-19? [yes/ no]	X
Protocol Language: Patients with serious intercurrent illness that requires active infusional therapy, intense monitoring, or frequent dose adjustments for medication including but not limited to infectious disease, cancer, autoimmune disease, cardiovascular disease.	Are you on any IV or other serious medications, such as chemotherapy? [yes/ no]	X
Protocol Language: Patients who have undergone major abdominal, thoracic, spine or CNS surgery in the last 2 months, or plan to undergo surgery during study participation.	Have you had any surgery in the last two months? [yes/ no]	X
Protocol Language: Patients currently taking digoxin	Do you take the medication, digoxin or lanoxin? [yes/ no]	X
(From Medication Section)	Have you ever had a seizures? [yes/ no]	X

PATCH 2 & 3 TRIAL

(From Medication Section)	Have you ever had a transplant? [yes/ no]	X
Protocol Language: History or evidence of increased cardiovascular risk including any of the following: 
 Left ventricular ejection fraction (LVEF) < institutional lower limit of normal. Baseline echocardiogram is not required; Current clinically significant uncontrolled arrhythmias. Exception: Subjects with controlled atrial fibrillation; History of acute coronary syndromes (including myocardial infarction and unstable angina), coronary angioplasty, or stenting within 6 months prior to enrollment; Current ≥ Class II congestive heart failure as defined by New York Heart Association. 	Do you have any heart disease such as congestive heart failure, history of heart attack, angina, arrhythmias or atrial fibrillation (also called AFib)? [yes/ no]	X

C STUDY LEAD DECIDED EXCLUSIONS

Consumer Language for Enrollment Exclusions

- These exclusions will be asked prior to the consent call through the study enrollment portal. “Yes” response do not trigger an automatic exclusion.
- “Yes” responses require a live conversation between the prospective participant and the study lead during live consent.
- If a medical consult is needed, then the study lead will conduct a medical consult with study PIs. Track all medical consult language in the study portal.
- Call the prospective study participant back with the final decision (yes or no) on enrollment. If he/she is eligible, then finish study consenting, and trigger tablet + journal shipment

DISEASE EXCLUSIONS

Protocol Language	Study Portal Language		
Eye Disease: Known retinal disease including but not limited to macular degeneration, retinal vein occlusion, visual field defect, diabetic retinopathy	Do you have eye disease? [yes/ no]		
	(if yes) Please describe. [open text]		
	INCLUDED IF:	MEDICAL CONSULTATION IF:	EXCLUSION IF:
	Wears eye glasses		Any eye disease

Protocol Language	Study Portal Language		
Lung Disease: History of interstitial lung disease, severe emphysema or asthma, or chronic pneumonitis unrelated COVID-19.	Do you have lung disease, such as asthma or emphysema? [yes/ no]		
	(if yes) Please describe. [open text]		
	INCLUSION IF:	MEDICAL CONSULTATION IF:	EXCLUSION IF:
	If moderate or controlled	If in question, then medical consult	If severe, then exclude

Protocol Language	Study Portal Language		
Porphyria and Psoriasis: Due to risk of disease exacerbation patients with porphyria or psoriasis are ineligible unless the disease is well-controlled, and they	Do you have porphyria? [yes/ no]		
	Do you have psoriasis? [yes/ no]		
	INCLUSION IF:	MEDICAL CONSULTATION IF:	EXCLUSION IF:

PATCH 2 & 3 TRIAL

are under the care of a specialist for the disorder who agrees to monitor the patient for exacerbations.	If moderate or controlled	If in question, then medical consult	If severe, then exclude
--	---------------------------	--------------------------------------	-------------------------

MEDICATION EXCLUSIONS

Study Portal Language	Please list all medications that you are currently taking [text fields- one per medication]
	
 The following medications are not allowed during the study. The sponsor must be notified if the participant receives any of these during the study. Participants must be instructed not to take any medications, including over the counter products, without first consulting with the investigator. IF a study participant sees another provider, they are instructed to bring their study journal to this provider visit. IN ADDITION, the participant should contact the study lead any time they seek medical treatment.

Drug Classes	Protocol Language
Anticonvulsant	
 (Exclude) Patients receiving cytochrome P450 enzyme-inducing anticonvulsant drugs (i.e. phenytoin, carbamazepine, Phenobarbital, primidone or oxcarbazepine) within 4 weeks of the start of the study treatment Acceptable drug alternatives include: Because HCQ has known effects on P450 enzymes, patients requiring anti-convulsants may be treated with any of the non-enzyme inducing anti-convulsants which include: felbamate, valproic acid, gabapentin, lamotrigine, tiagabine, topiramate, or levetiracetam. Due to the fact that both zonisamide and HCQ accumulate in red blood cells, zonisamide should be avoided if possible. All other concomitant medications are permitted.
Antiviral	
 (Exclude) Any investigational or off-label antiviral therapy (Include) Patients with HIV may participate (Include) Patients with herpes may participate
Cancer Treatments	
 (Exclude) Anyone receiving active cancer treatments. (Exclude) Any concurrent chemotherapy, radiotherapy (except radiotherapy as designated in this study or radiotherapy indicated for CNS metastasis) (Exclude) Immunotherapy, (Exclude) Biologic or hormonal therapy for cancer treatment, except as noted in the exclusion criteria. (Include) A Cancer survivor receiving no treatments may participate (Include) Concurrent use of hormones for non-cancer-related conditions (e.g. insulin for diabetes, hormone replacement therapy).
Immunosuppressive	
 (Exclude) Immunosuppressive medications, including, corticosteroids at doses exceeding 10mg/day of prednisone or equivalent, methotrexate, azathioprine, and TNF-alpha blockers. (Include) Use of immunosuppressive medication for the management of study treatment related AEs or in subjects with contrast allergies is acceptable. (Include) In addition, use of topical, inhaled and intranasal corticosteroids is permitted.
Live attenuated vaccines	
 (Exclude) If using live attenuated vaccines during the study through 180 days after the last dose of both drugs. Examples include: MMR, Zostavax, Polio, Varicella (Include) If using non-living vaccines. Examples include: Flu vaccine, Pneumonia vaccine
Insulin or antidiabetic drugs	
 Reduce dosage consideration. As HCQ may enhance the effects of a hypoglycemic treatment, a decrease in doses of insulin or antidiabetic drugs may be required.
Arrhythmogenic	
 Drugs that prolong QT intervals. HCQ can prolong the QT interval and should not be administered with other drugs that have the potential to induce cardiac arrhythmias. Also, there may be an increased risk of inducing ventricular arrhythmias if HCQ is used concomitantly with other arrhythmogenic drugs

PATCH 2 & 3 TRIAL

Antiepileptics	
 Side effect. The activity of antiepileptic drugs might be impaired if co-administered with HCQ.
Cyclosporin	
 Side effect. An increased plasma cyclosporin level was reported when cyclosporin and HCQ were co-administered

See **medication look up tool** for inclusion or exclusion guidance related to specific medications

PATCH Medication Look-Up Tool

If a prospective participant is on any of the following medications listed below, it is an **automatic study exclusion** due to the known interactions with HCQ.

Directions: To check if a patient's medication is on this list, select on the drop down icon [v] by drug name and/or brand name. In the box, there is a search bar where you type to find whether the medication is on the exclusion list. If found, the participant is excluded from this study.

Drug Name	Brand Name	Interaction Level	Evidence Level for Drug Interaction (Source: Lexicomp, Medscape)	Study Determination
ALFUZOSIN	UROXATRAL	Major	Good	Study Exclusion
AMITRIPTYLINE	ELAVIL	Major	Good	Study Exclusion
ANAGH-100	ANAGYLIN	Major	Good	Study Exclusion
APOMORPHINE	APOMORIN	Major	Good	Study Exclusion
ARIPRAZOLE	ABILIFY	Major	Good	Study Exclusion
ARSENIC TRIOXIDE	NONE	Major	Good	Study Exclusion
ASENAPINE	SAPHRIS	Major	Good	Study Exclusion
ASPIRIN/810 F	NONE	Major	Good	Study Exclusion
ATAZANAVIR	REYVALZ	Major	Good	Study Exclusion
AZITHROMYCIN	ZITHROMAX, Z-PAK	Major	Good	Study Exclusion
BEDAQUILINE	SIRTURO	Major	Good	Study Exclusion
DEPRIDIL	VASCOR	Contraindication	Good	Study Exclusion
RUSSERLIN	SUPREFACT	Major	Good	Study Exclusion
CHELOXOLINE	NONE	Major	Good	Study Exclusion
CHLORPROMAZINE	THORAZINE	Major	Good	Study Exclusion
CIPROFLOXACIN	CIPRO	Major	Good	Study Exclusion
CISAPRIDE	NONE	Contraindication	Good	Study Exclusion
CITALOPRAM	CILEXA	Major	Good	Study Exclusion
FLARITHAMININ	SILOXIN	Major	Good	Study Exclusion

D EMERGENCY INDICATIONS

EMERGENCY SYMPTOMS (911)	Protocol Language
	
Participants will be instructed to call 911 upon immediate presentation of the following symptoms as identified by the CDC as requiring emergency action:
 
 Bluish lips or face New confusion/dizziness or inability to arouse Persistent pain or pressure in the chest (not caused by coughing) Difficulty breathing (including severe shortness of breath and single word speech)

E SIDE EFFECT GUIDE

[figure not shown]

Directions

- Ask the study doctor if you have questions about the **signs or symptoms of any side effects**.
- Please tell the study doctor or study staff right away if you have any **side effects**.
- Please tell them if you have any other **problems with your health** or the way you feel during the study, whether or not you think these problems are related to the study drugs.

Serious	Protocol Language
Side effects occurring at a frequency which cannot be estimated from available data	
 • Convulsions • Heart problems (e.g. breathlessness with exercise or even at rest, swelling of the legs, ankles and feet, irregular heartbeats that feel rapid or pounding, chest pain, sudden fainting) • Hypoglycemia (low blood sugar) (e.g. sweating, shakiness, weakness, dizziness, fast heartbeat, nausea, irritability, blurred vision, confusion, loss of consciousness) • Increased sensitivity to sunlight. Skin rash due to sunlight can be reduced by appropriate use of sunscreen creams • Liver problems with symptoms such as: unusual tiredness, nausea, vomiting, abdominal pain, or jaundice (yellow discoloration of the eyes or skin) • Long-lasting involuntary muscle contraction; impairment of voluntary movements, tremor • Lowered blood cell counts (e.g. fatigue, weakness, increase susceptibility to infections or bleeding) • Muscle weakness • Psychosis (e.g. hallucinations, loss of contact with reality) • Severe breathing problem (bronchospasm, angioedema) • Severe skin problem • Suicidal thoughts
Rare	Protocol Language
These occurring in 0.1 to 1% of participants receiving this drug	
 • Dizziness • Hair loss or bleaching of hair • Loss of skin pigment or increase in skin pigment (bluish-black color) • Nerve and muscle disorders (e.g. tingling, numbness, burning pain, weakness, cramps, and spasms) • Ringing in the ears, decreased hearing
Common	Protocol Language
These occur in 1 to 10% of participants receiving this drug	
 • Diarrhea • Vomiting • Loss or lack of appetite (anorexia) • Headache • Nervousness, emotional changes • Rash, itchy rash • Visual problem: blurred vision, difficulty focusing, seeing halos around lights, especially at night, seeing light flashes and streaks, night blindness, visual field loss, change in eye color (eye pigmentation), difficulty focusing eye, difficulty reading (skipped words). • Notes on Vision: HCQ may rarely cause problems with your vision. A review of over 1000 patients taking HCQ found that this side effect occurred in only 1 patient and only after they had taken the drug for 7 years. Vision problems include visual disturbances such as flickering or flashing lights, dimming of your vision (things appear darker) and decreased vision that could progress to blindness.
Very Common	Protocol Language
These occur in 10% or more of participants receiving this drug	
 • Nausea • Stomach pain • Stomach cramps

F. PATCH3 HEALTH CARE WORKER WELCOME KIT

[figure not shown]
[figure not shown]
Shipment 1:

Content	Description
	
THE MEDICATION BOTTLE
 
Blinded - 90 tabs
 
Medication ID: [bottle serial number]
 
Contents: 90 tablets
 
Instructions: Take 3 tablets in the AM daily for a total of 30 days. One refill will be shipped to you.
 
Store at [insert storage instructions from the manufacturer]
 
Caution: New Drug - Limited by Federal (or United States) law to investigational use

	
THE HYDOXYCHLOROQUINE MEDICATION GUIDE
 
 The HCQ Medication Guide opens with: “You have received your medication tablets in this box. These tablets may be a placebo or they may be the active hydroxychloroquine (HCQ) medication. Below is a list of possible side effects from taking active HCQ.”
	
THE STUDY JOURNAL
 
 15 page Study Journal Includes a variety of study information, contact information, FAQ, reminders and study tracking examples
	
A THERMOMETER
 
 A thermometer will be sent to all health care worker participants to track their temperature It will be all white
	
PEN
 
 An ink pen will be sent to all health care workers to use with the study journal

[figure not shown]
[figure not shown]
PATCH 2 & 3 TRIAL

	
REMINDER CARD

	
 The reminder card is to help remind health care workers to get their weekly oxygen level checked at work and track the number of hours they missed due to their own COVID-19 symptoms

Shipment 2:

Content	Description
	
THE MEDICATION BOTTLE

	
Blinded - 90 tabs Medication ID: [bottle serial number] Contents: 90 tablets Instructions: Take 3 tablets in the AM daily for a total of 30 days. One refill will be shipped to you. Store at [insert storage instructions from the manufacturer] Caution: New Drug - Limited by Federal (or United States) law to investigational use

	
THE HYDOXYCHLOROQUINE MEDICATION GUIDE

	
 The HCQ Medication Guide opens with: “You have received your medication tablets in this box. These tablets may be a placebo or they may be the active hydroxychloroquine (HCQ) medication. Below is a list of possible side effects from taking active HCQ.”

PATCH3 HEALTH CARE WORKER CROSSOVER KIT

Content	Description
	
CROSSOVER MEDICATION Unblinded Active HCQ - 42 tabs Medication ID: [bottle serial number] Contents: 42 tablets Directions: Take 3 pills in the AM daily for 14 days. No refill. Store at [insert storage instructions from the manufacturer] Caution: New Drug - Limited by Federal (or United States) law to investigational use

	
CROSSOVER GUIDE This guide is to support the health care worker with instructions when crossing over from placebo to HCQ should they qualify.

E FREQUENTLY ASKED QUESTIONS (FAQ)

Type of Question	Question	Response
Study Info	What is the PATCH Study?	PATCH, also known as Prevention and Treatment of COVID-19 with Hydroxychloroquine (HCQ), is a research study that is being conducted by ProHEALTH NY, University of Pennsylvania, and UnitedHealth Group Research & Development to determine if HCQ can be an effective antiviral medication for preventing and treating COVID-19.
Study Info	What will be expected of me if I decide to participate in this study?	A package will be sent to you with either HCQ active or placebo pills. We ask that you take your medication according to the package direction, check your temperature twice daily or report symptoms of fever, record and report any adverse events, and upload this information daily through the study portal at patchstudy.com for the full duration of this study. You'll also be asked to get your swab samples taken at the end of the study.
Study Info	Can anyone join?	The PATCH2 Study is focused on recruiting patients who are: 
 • between the ages of 50-75 years of age • experiencing COVID-19 symptoms such as cough, fever, and/or sore throat • being sent home for a 14-day self-quarantine after being tested for COVID-19

PATCH 2 & 3 TRIAL

